### 3.2.2.3 Analysis Methods

#### A. Statistical Methodology

The Kaplan-Meier method will be used to estimate the probability of a subject experiencing one or more CPE at 12 months follow-up. The standard error will be approximated using Greenwood's formula. A two-sided 95% log-log confidence interval for the probability will be constructed. The Kaplan-Meier estimate and its 95% log-log confidence interval will be constructed from the day of study specified cryoablation procedure (Day 0) through the end of follow-up. For subjects with safety events, the days of follow-up will be computed as the days from Day 0 to the onset date of the first safety event. For subjects without safety events, days of follow-up will be computed as the days from Day 0 through the last follow-up. For subjects who are lost to follow-up, the last contact date will be used as the last follow-up date.

The 12 month visit may occur after 365 days since the visit window runs until 30 days past day 365. Not including events that result from assessment at a 12 month visit, but after day 365 could underestimate the proportion at 1 year due to 12 month visits that occur after 365 days. This potential bias is addressed in the statistical analysis by considering the date of recurrence to be exactly 12 months (365 days) from the study ablation procedure so that these events will be counted as SPE in the 12-month Kaplan-Meier analysis.

#### B. Determination of Subject s/Data for Analysis

The analysis will be conducted using the modified intent-to-treat (mITT) set.

[figure not shown]
### 3.2.2.4 Sample Size Methods and Assumptions

Sample size was estimated using SAS v9.2 Proc Power. The sample size was calculated under an asymptotic z-test for a single binomial proportion with a continuity adjustment under the following assumptions:  
Power = 90%, Significance level = 0.025 (one-sided), Assumed underlying primary safety event rate = 6%, Performance goal = 14.8%.

The performance goal of 14.8% is selected based on the same assumption defined in version 1.7 of the STOP AF Clinical Investigation plan (January, 2008): "Based on a review of SSEDs for similar types of ablation trials, the expected rate for CPEs in a well-monitored trial of left atrial RF ablation for AF was estimated to be 10% (corresponding to a CPE-free rate of 90%). If 16 of 160 subjects were observed to have at least one CPEs then the resulting one-sided 95% upper confidence bound would be 14.8%."; where SSED is an abbreviation for Summary of Safety and Effectiveness Data.

Figure 3 presents the sample size at different primary safety event rates under the assumptions outlined above.

Figure 3. Sample Size vs. Primary Safety Event Rate

If the underlying safety event rate is assumed 6%, a total of 141 evaluable/mITT subjects will be required to provide 90% power to meet this safety objective.

### 3.3 Secondary Objectives

All secondary analyses will be exploratory and no formal hypotheses tested.

#### 3.3.1 Secondary Objective #1 (Effectiveness Objective)

The probability of subjects free of chronic treatment failure at the and 2 year follow-up visits will be estimated.

##### 3.3.1.1 Hypothesis

There is no hypothesis.

##### 3.3.1.2 Endpoint Definition

Chronic treatment failure is defined in Primary Objective #1, section 3.2.1.2. Subjects free of chronic treatment failure are those that do not meet that definition.

**3.3.1.3 Analysis Methods**

**A. Statistical Methodology**

The Kaplan-Meier method will be used to estimate the probability of chronic treatment success at 1 and 2 year follow-ups. The standard error will be approximated using Greenwood's formula. Two-sided 95% log-log confidence intervals for the probability will be constructed for each of the four followups. The Kaplan-Meier estimates and their 95% log-log confidence intervals will be constructed from the day of protocol specified ablation procedure (Day 0) through the end of followup. For subjects with a treatment failure, the days of followup will be computed as the day from Day 0 to the failure date. For subjects without failure events, days of followup will be computed as the days from Day 0 through the last followup. For subjects who are lost to followup, the last contact date will be used as the last followup date.

**B Determination of Subject s/Data for Analysis**

The estimations will be conducted using the modified intent-to-treat (mITT) set.

**3.3.2 Secondary Objective #2 (Major Atrial Fibrillation Events)**

The probability of subjects free of Major Atrial Fibrillation Events (MAFE) at the 1 and 3 year follow-up visits will be estimated.

**3.3.2.1 Hypothesis**

There is no hypothesis.

**3.3.2.2 Endpoint Definition**

Major Atrial Fibrillation Event (MAFE): A MAFE is a serious adverse event (SAE) which has not been categorized as a CPE as set out in the following table:

**Table 2: Major Atrial Fibrillation Events**

Major Atrial Fibrillation Events (MAFEs):
Cardiovascular deaths
Hospitalizations for (primary reason): AF recurrence or ablation Atrial flutter ablation (excluding Type I) Systemic embolization (not stroke) Congestive heart failure Hemorrhagic event (not stroke) Antiarrhythmic drug: initiation, adjustment or complication
Myocardial infarction (MI)
Stroke

### 3.3.2.3 Analysis Methods

#### A. Statistical Methodology

The Kaplan-Meier method will be used to estimate the probability of a subject being free of MAFE at 1, 2, and 3 year follow-ups. The standard error will be approximately using Greenwood's formula. Two-sided 95% log-log confidence intervals for the probability will be constructed for each of the five follow-ups. The Kaplan-Meier estimates and their 95% log-log confidence intervals will be constructed from the day of study specified cryoablation procedure (Day 0) through the end of each follow-up. For subjects with a MAFE, time until an event will be computed as the number of days from Day 0 to the onset date of the first MAFE. For subjects without a MAFE, the number of days at-risk will be computed as the days from Day 0 through the last time they had an opportunity to report a MAFE, which includes scheduled study follow-up visits and their associated testing plus the termination visit, if done. For subjects who are "lost to follow-up", time from Day 0 until last contact date will be used as the number of days at risk.

#### B. Determination of Subject s/Data for Analysis

The estimations will be conducted using the modified intent-to-treat (mITT) set.

### 3.3.3 Secondary Objective #3 (Long Term Safety Outcomes)

Device and procedure related events, serious adverse events (SAE), and other safety categories will be collected through the 3 year follow-up and reported descriptively.

#### 3.3.3.1 Hypothesis

There is no hypothesis.

#### 3.3.3.2 Endpoint Definition

Device and procedure related events, and SAEs are defined in section 7.2.1 dCIP version 6.

#### 3.3.3.3 Analysis Methods

##### A. Statistical Methodology

For each event, the total number of events, the number of subjects with at least one event, and the percentage of subjects with at least one event will be reported. Totals and sub-totals will be reported in the same manner. All of these events will be categorized using the MedDRA or similar system, tabulated and listed in decreasing frequency order.

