## 2 RATIONALE FOR STUDY DESIGN

### 2.1 Study Purpose

The pivotal trial (STOP -AF) of the Arctic Front® Cardiac Cryoablation Catheter System with the adjunctive use of the Freezor® MAX Cardiac Cryoablation Catheter to electrically isolate pulmonary veins (PV) in patients with paroxysmal atrial fibrillation (PAF), compared to a randomized drug control group has been performed and a final report submitted to the FDA resulting in product approval December 2010. A Continued Access Protocol trial (CAPAF) was also conducted to allow collection of additional safety data following modifications implemented into the Arctic Front® Catheter and Cryoablation System. As part of the continued clinical development of the Arctic Front® Cardiac Cryoablation Catheter System, this Post Approval Study (PAS) is being conducted to provide long-term safety and effectiveness monitoring/data per the Pre-Market Approval order (P100010) by the Food and Drug Administration (FDA).

This PAS is a prospective multicenter, non-randomized, single arm, controlled, unblinded clinical study of up to 400 enrolled subjects with PAF who have failed one or more Atrial Fibrillation Drugs (AFDs). All study subjects will be receiving cryoablation with the study devices and, optionally (post-procedure), an Atrial Fibrillation Drug.

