##### B. Determination of Subject s/Data for Analysis

The population(s) used for descriptive summarization will be the mITT set.

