## 4 APPENDIX

### 4.1 Overall Sample Size

In order to adequately power for both the primary effectiveness and safety hypotheses, we require a sample size of 270 evaluable subjects to complete 36 months of follow-up. We estimate that the attrition rate will be approximately 10% per year for the duration of the originally intended 5 year follow-up period. Therefore, the final sample size required to achieve 270 subjects followed for 36 months and account for attrition (i.e. 10% per year) is 370 mITT subjects with procedure attempts. It is expected up to 400 subjects will need to be enrolled to ensure 370 mITT subjects with procedure attempts assuming a small number of subjects who are enrolled will not undergo a procedure.

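### Long-term safety (Secondary Objective #3) is summarised as crude percentages that ignore early exit and have no fixed horizon, so late risk can be understated

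*SAP*

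**What the plan says.** SAP 3.3.3 (Long Term Safety Outcomes) covers device- and procedure-related events, SAEs and other safety categories, which "will be collected through the 3 year follow-up and reported descriptively". The method in 3.3.3.3 is the number of events per category and then "the number of subjects with at least one event, and the percentage of subjects with at least one event will be reported", with totals and sub-totals handled the same way. On the denominator: "The population(s) used for descriptive summarization will be the mITT set". No number at risk, time-to-event estimate or exposure-adjusted rate is planned for this objective.

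Three other places bear on this:

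- SAP 4.1: "We estimate that the attrition rate will be approximately 10% per year for the duration of the originally intended 5 year follow-up period". The same section states "we require a sample size of 270 evaluable subjects to complete 36 months of follow-up" and concludes that the number needed "is 370 mITT subjects with procedure attempts".
- SAP 2.2: follow-up was cut from 5 to 3 years, but year 4 and 5 data from subjects already seen at those visits go into the safety summary.
- SAP 2.1: "this Post Approval Study (PAS) is being conducted to provide long-term safety and effectiveness monitoring/data".

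Elsewhere the SAP does allow for exits. CPE is estimated by Kaplan-Meier at 12 months (3.2.2.3) and MAFE, a listed class of SAEs, by Kaplan-Meier at 1, 2 and 3 years (3.3.2.3).

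**The concern.** In a crude percentage, a subject who leaves at month 6 without an event stays in the denominator as though observed event-free to the end. Events around the procedure are counted almost in full, while events in the second and third years are missed in proportion to the subjects already gone. A long-term safety objective is most interested in that later period.

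SAP 3.1.4.2 expects missing data to matter little because the primary objectives use Kaplan-Meier. That argument does not extend to Objective #3, and no imputation is planned. The year 4-5 data pull the other way: they add events from a subset followed for longer. The result is a percentage with no defined horizon, which cannot be set beside the Kaplan-Meier CPE and MAFE figures in the same report. At stake is how late risk reads in a study whose stated purpose includes long-term safety.

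**Working it through.** **Inputs from SAP 4.1.** Attrition 10% a year; 270 subjects at 36 months; 370 mITT subjects at the start.

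**Plan's own figure.** 270 / 0.9³ = 270 / 0.729 = 370.4, against 370 stated. It reproduces, so the 10% is compounded over three years. Expected exit by 3 years is 1 − 0.729 = 27.1%.

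**Assumptions, not in the SAP.** Exits occur at a constant rate and are unrelated to risk; the event hazard is constant; no year 4-5 data enter. The SAP gives no event-time distribution, so these serve only to size the effect.

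**Events over 0-3 years.** Exit hazard c = −ln(0.9) = 0.1054 a year. For a true 3-year risk I, the event hazard is L = −ln(1 − I)/3, and the crude share is L/(L + c) × [1 − exp(−3(L + c))].

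- I = 10%: L = 0.0351, so 0.25 × (1 − 0.9 × 0.729) = 0.25 × 0.3439 = 8.6%, which is 14.0% low (1.4 percentage points).
- I = 20%: 17.3%, which is 13.8% low.
- I = 30%: 26.0%, which is 13.5% low.
- Rare-event limit: 1 − 0.271/(3 × 0.1054) = 14.3% low.

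**Events arising only in years 2-3.** L = −ln(1 − I)/2, and the crude share is 0.9 × L/(L + c) × [1 − exp(−2(L + c))].

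- I = 10%: 0.9 × (1/3) × 0.271 = 8.1%, which is 18.7% low.
- I = 20%: 16.3%, which is 18.5% low.

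**Sensitivity to timing.** If a fraction f of a category occurs around the procedure and the rest evenly over 3 years, the shortfall is (1 − f) × 14.3%: 7.1% for f = 0.50, 3.6% for f = 0.75 and 1.4% for f = 0.90.

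**Sensitivity to attrition (rare events).** At 5% a year the shortfall is 7% over 0-3 years and 10% for years 2-3. At 3% a year it is 4% and 6%. If all exits fall at the end of each year at 10%, it is 10% and 15%.

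**Effect of year 4-5 data.** Let g be the share of 3-year completers who go on to contribute years 4-5 (assumed; the SAP gives no figure), with the same yearly attrition and rare events at a constant hazard. The ratio of the crude percentage to the true 3-year risk is [0.271 + g × (0.729 − 0.590)] / (3c). That gives 0.90, 0.95 and 0.99 for g = 10%, 20% and 30%. It passes 1 at g of about 33%.

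**The case against.** The strongest reply is that the SAP follows a consistent convention: Kaplan-Meier for defined, adjudicated endpoints, and counts with percentages for adverse-event tables. The all-AE summary in 3.3.6.3 is crude too. Nothing in 3.3.3.3 calls its percentages 3-year risks, and all secondary analyses are exploratory. That stands, and it is why this is an improvement rather than an error that affects a conclusion. It does not fully explain the omission, since MAFE is equally exploratory and gets Kaplan-Meier estimates.

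A reader might infer that long-term safety as a whole is reported only crudely. The SAP does not support that. MAFE takes in cardiovascular death, stroke, MI and several kinds of hospitalisation, all estimated to 3 years with censoring handled, and CPE is handled the same way at 12 months.

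Two further points stand. The 10% is an approximate planning figure, and actual exit may be lower. SAP 4.1 also does not say whether it includes deaths. If it does, part of the dilution is not bias for a non-fatal event analysed with death as a competing event, because a subject who dies first properly stays in the denominator.

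**Conclusion.** The point holds in limited form. Objective #3 gives no fixed-horizon estimate that allows for exit for three groups: any SAE overall; SAEs that are neither MAFE nor CPE; and device- or procedure-related events that occur after 12 months or are not classed as CPE. For these, crude percentages can understate late risk.

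The size is conditional: about 14% relative over 0-3 years and about 19% for events confined to years 2-3, given the assumed attrition, non-informative exit, a constant hazard and no year 4-5 data. It would be tempting to read 14-19% as a fixed property of the plan, but the SAP does not support that. Most CPE onset windows in Table 1 are 7 days, which suggests that procedure-related events cluster early, and for mostly periprocedural categories the figure is about 1-7%. The year 4-5 data could offset the shortfall or, above roughly one third of completers under the assumptions used, reverse it. The direction of the net error against a 3-year risk is therefore not certain; the lack of a fixed horizon is.

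No hypothesis, performance goal or success criterion depends on these tables. Low severity, cheap to improve.

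**What to change.** In SAP 3.3.3.3:

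1. Keep the planned counts and percentages by MedDRA term, and label the percentages as observed proportions rather than 3-year risks.
2. For any SAE, any device-related event and any procedure-related event, add cumulative incidence at 1, 2 and 3 years with 95% confidence intervals and numbers at risk. Use Kaplan-Meier, or Aalen-Johansen with death as a competing event for non-fatal categories.

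Estimates at fixed times deal with both early exit and the year 4-5 data. Events in years 4-5 stay in the counts but do not enter the 3-year figure.

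The cost is a few lines of SAP text and one extra table, using the same kind of onset and last-contact dates that the CPE and MAFE analyses already need. The downside is that the reported 3-year figures may look slightly less favourable than the crude ones.

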### 2.2 Study Scope

The study is expected to enroll subjects over an 18 - 24 month period with post procedural follow-up consisting of clinic visits at 6 and 12 months, and 2 and 3 years. There was a CIP change in June of 2016 that reduced the follow up time of this study from 5 years to 3 years. Prior to sites' activation of version 6 of the CRF, some subjects may also have been seen at 4 year or 5 year visits. This data will be included in the summary of safety outcomes.

Since the primary endpoint of the study is assessed at 3 years, the power of the study is not affected by this change.

More than 30 investigational sites in the United States and Canada have participated in this investigation. The Principal Investigator is [name] at Northwestern Memorial Hospital in Chicago, Illinois.

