#### 3.3.6.2 Endpoint Definition

All adverse events that occur during the study will be captured on the CRFs.

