##### B. Determination of Subjects/Data for Analysis

The population used for descriptive statistics will be the enrolled set. Summaries will be presented for both the Intent-To-Treat (ITT) Set and Modified Intent-To-Treat (mITT) Set.

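### The Objective #3 long-term safety table leaves out treated but ineligible subjects, and it may count year 4-5 events over the whole mITT set although the objective stops at 3 years

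*SAP*

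**What the plan says.** **Objective #3.** Section 3.3.3 covers device- and procedure-related events, serious adverse events and other safety categories, which "will be collected through the 3 year follow-up and reported descriptively". Section 3.3.3.3 A asks for the number of events and the number of subjects with an event, and adds that "the percentage of subjects with at least one event will be reported". Section 3.3.3.3 B fixes the denominator: "The population(s) used for descriptive summarization will be the mITT set".

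**Year 4-5 data.** Section 2.2 explains that follow-up was shortened from 5 to 3 years in 2016 and that, before sites changed over, "some subjects may also have been seen at 4 year or 5 year visits". It then instructs: "This data will be included in the summary of safety outcomes". It names no objective or table.

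**Analysis sets.** Under section 3.1.1, ITT requires that all eligibility criteria are met. mITT is the part of ITT in which the catheter system was inserted. The All Treated Set requires only consent and insertion. Section 4.4 confirms that a treated subject who fails a criterion is in neither ITT nor mITT, calls this rare, and makes a repeat analysis on All Treated discretionary.

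**Objective #6 (all adverse events).** Section 3.3.6.2 has no 3-year limit: "All adverse events that occur during the study will be captured on the CRFs". On the population, section 3.3.6.3 B says "The population used for descriptive statistics will be the enrolled set" and then "Summaries will be presented for both the Intent-To-Treat (ITT) Set and Modified Intent-To-Treat (mITT) Set".

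**The concern.** Section 2.1 gives long-term safety monitoring as a reason for this post-approval study, and Objective #3 is the section that carries it by title. Two features weaken its table.

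- **Population.** Eligibility is a reasonable filter for an effectiveness analysis. In a safety table it removes people who were exposed to the device. A device- or procedure-related event in a treated but ineligible subject has no place in the Objective #3 table as planned.
- **Time.** Section 3.3.3 closes the window at 3 years, while section 2.2 adds later data from an unspecified part of the cohort. If the later events go into the same table, its percentage mixes events that the whole mITT set was meant to be followed for with events that only a later-followed subset could have. Such a percentage refers to no defined length of follow-up.

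Two analysts working from this text could therefore report different long-term percentages. They could also differ on whether treated but ineligible subjects appear in any safety table.

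**Working it through.** **1. Who is in the Objective #3 table (sections 3.1.1, 3.3.3.3 B and 4.4).**

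| Set | Consent | All eligibility criteria met | Catheter inserted |
|---|---|---|---|
| Enrolled | yes | not required | not required |
| ITT | yes | required | not required |
| mITT | yes | required | required |
| All Treated | yes | not required | required |

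All Treated minus mITT is the group of treated but ineligible subjects. Objective #3 uses mITT, so that group is absent from numerator and denominator alike. The SAP gives no number for it, so the effect on any percentage cannot be computed and none is claimed.

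**2. Which time window applies (sections 2.2, 3.3.3 and 3.3.6.2).** Section 3.3.3 ends at the 3-year follow-up. Section 2.2 sends year 4-5 data to a safety summary. The nearest match by title is Objective #3, which is closed at 3 years. Objective #6 has no time limit and could take the events, but section 2.2 does not point to it. The destination is left to the analyst.

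**3. Which denominator late events would have.** In Objective #3 it would be the full mITT set, since section 3.3.3.3 B gives no other rule.

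**4. Illustration from the SAP's own planning figures (section 4.1).** Inputs: 370 mITT subjects, attrition of about 10% per year, 270 subjects followed for 36 months.

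- Reproducing the plan: 270 / 0.9³ = 270 / 0.729 = 370.4, which agrees with the stated 370. In the other direction, 370 × 0.729 = 269.7, about 270.
- Ratio of the mITT denominator to those planned to remain at year 3: 370 / 270 = 1.37.

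The 1.37 is not a bound. It depends on the planned attrition: at an assumed 5% per year, 370 × 0.95³ = 317 and 370 / 317 = 1.17. In the other direction, section 2.2 says only that some subjects were seen in years 4-5, so the number followed then may be well below the number remaining at year 3. The SAP does not give it, and the true ratio cannot be derived from the document.

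**The case against.** **The two time statements are a rule and its exception.** Section 3.3.3 describes collection under the shortened plan, section 2.2 deals with data already in hand, and the wording of section 2.2 is close to the title of Objective #3. This is a fair reading, and it reduces the conflict to a missing cross-reference. It also makes the denominator problem actual, because on this reading late events do enter a table whose percentage is taken over all mITT subjects.

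**A denominator is assigned.** A reader might infer that year 4-5 data have none. That goes too far: mITT is the default for Objective #3. What is missing is a rule for the subset followed past year 3.

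**The size is unknown.** A reader might treat 270 as the most who could have a late event, or assume a share of subjects seen in years 4-5 and obtain much larger ratios. The documents support neither. The 270 is a planning target, and no count of late visits is given. Event and subject counts do not depend on the denominator.

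**Crude percentages are legitimate here.** A reader might infer that the table understates 3-year risk because it ignores censoring. The table does not claim to estimate risk, and the SAP already plans Kaplan-Meier estimates for procedure events and for major AF events. Nothing is held against the crude percentage as such.

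**Objective #6 may cover the excluded subjects.** The enrolled set includes them, section 3.3.6.3 A allows seriousness and relatedness to be shown as appropriate, and the sentence on ITT and mITT can be read as adding summaries. This is the more natural reading, so the point on Objective #6 is one of loose wording. It does not repair the Objective #3 table, where the exclusion is certain.

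**Conclusion.** The point holds for descriptive safety reporting. The exclusion of treated but ineligible subjects from the Objective #3 table follows directly from the set definitions. The handling of year 4-5 events is unsettled, and under the most natural reading of section 2.2 they would be divided by a group that was largely not under observation in those years or not known to have been.

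No size is claimed for the first part, because the group is described as rare and not counted. For the second, the 1.37 is an illustration that assumes the planned 10% yearly attrition. The actual figure depends on how many subjects were followed in years 4-5.

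The secondary analyses are exploratory (section 3.3), so no primary conclusion, power or error rate is touched. The change is still worth making: it replaces stated rules with better ones in a study whose purpose includes long-term safety, and it uses a set that the SAP already defines.

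**What to change.** 1. **Objective #3 population (section 3.3.3.3 B).** Use the All Treated Set for the table. An mITT version may be kept alongside.
2. **Objective #3 time window (sections 2.2 and 3.3.3).** Cut the main table at the 3-year visit. Report year 4-5 events in a separate table whose denominator is the number of subjects followed in those years. Reword both sections so that they agree and section 2.2 names that table.
3. **Objective #6 (section 3.3.6.3 B).** Keep the enrolled set, so that adverse events in enrolled subjects who never had a procedure are not lost; All Treated would drop them. State that the ITT and mITT summaries are additional, and say whether year 4-5 events are included.

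The cost is a few sentences in the SAP and a few extra tables, with no new data. The downside is a slightly longer safety output.
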